Group assignment will be based on serial admissions meeting study inclusion / exclusion criteria. Randomization as described above is expected to achieve group equivalence in: 1) the first pain severity score obtained using the Numeric Analogue Scale measured during the1st exam prior to the first wound care session in the Burn Center; 2) the TBSA; 3) the need for surgery; 4) the average length of wound care procedures and; 5) "other" variables, including the distribution of baseline symptom severity of acute stress disorder, depression, anxiety, and insomnia (which will all be assessed at study enrollment before the first target dressing change). Baseline data on participants will be recorded, and comparability between study groups will be examined at 25% (n=  $\sim$ 19-24/group) and 50% (n=  $\sim$ 37-47/group) of study completion to assess presence of balancing issues. These same data will also be examined upon study completion (n= 74-94), and their relationship with core outcome targets will be examined. If necessary, their effect will be taken into consideration in planned analyses.

It is anticipated that, given the large sample size, the process of random assignment will ensure adequate balancing across study conditions (Usual Care Condition, Usual Care PLUS Ketamine Augmentation Condition) of potentially confounding variables. That is, for example, participants differing by clinically important variables such as smaller versus larger burns should be equally represented in both groups. The large sample size and the process of random assignment are deemed more than adequate to ensure representation across the two study arms for the differences in important but extraneous variables such as procedure duration and other aspects of wound care, rehabilitation and surgery.

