# 7. Study Statistics

- a. Primary outcome variable. Described above (Outcomes)
- b. Secondary outcome variables. Described above (Outcomes)
- c. Statistical plan including sample size justification and interim data analysis. Described above

Statistical consultation and initial power estimation were obtained from the Johns Hopkins Biostatistics, Epidemiology, and Database program (BEAD). The Johns Hopkins Institute for Clinical and Translational Research (ICTR) worked with the Ketamine Team to develop the randomization model and the REDCap Database and will continue to serve as consultants throughout the duration of the study. The ICTR expertise will be of particular importance when managing issues such as data cleaning and preparation, preparing interim reports, and in designing and conducting both preliminary and final statistical analyses. Using standard methods, the BEAD suggested that a total sample size of 74-94 participants (n= 37-47 per Condition) should be sufficient to provide a power of .85 to detect a statistically significant difference at p < 0.05. This study team has discussed this issue of power and decided to be conservative and enhance the opportunity of making a definitive statement regarding study objectives and secondary questions. Therefore, the total target sample size will be increased to n= 100. One clarification is important: Funding is for a 1-year period. Should funding end before 94 participants are enrolled the study will have more than sufficient power to address the primary objectives (n=74).

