# Data Analysis Plan

[name], a professional biostatistician from the JH BEAD program specializing in clinical trials and longitudinal data analysis, had assisted Drs. [name] and [name] in conducting the statistical analyses in consultation with Going forward, this role will be assumed by biostatisticians at the JHU-ICTR.

The primary data analyses (Pain variables) will be conducted using analysis of covariance, or, longitudinal growth modeling (if normality assumptions are met) to examine group differences both in cross-section and longitudinally. If normality assumptions are violated then appropriate nonparametric tests will be utilized (e.g., Wald statistic). These methods allow for statistical controlling multiple potential confounding baseline variables and are robust against dropout - expected to be minimal. Data from the following study were used to generate this power estimate (Beaudoin, 2014).

Prior to study start-up, it is anticipated that, since ANCOVA is the recommended procedure for analyzing pre- to post- treatment change scores, that is the test that will be utilized for the primary aim, because: it is more powerful than t-test and Mann-Whitney; it can adjust for baseline group differences; it can be adjusted for baseline randomization strata; and, it can be utilized in analyzing repeated measures such as in the present study.

Prior to testing hypotheses, univariate distributions of variables will be inspected to assess normality, identify outliers, skewness or other abnormalities in distribution, determine appropriate summaries of location and spread and the need for transformation or nonparametric analysis. Preliminary analyses will determine whether the data meet basic assumptions for parametric tests. If relevant covariates are not balanced by the randomization, or confounds are distributed unevenly across groups, they will be included in the models as covariates.

If Pain Intensity is substantially associated with non-study factors (e.g., age, gender, TBSA) these variables will be statistically controlled as indicated in analyses.

The data on average (or summed) Opiate Sparing Effects from baseline to post-treatment, and within group and between group changes over time are likely not to meet criteria for parametric analysis, that is, they are expected to be non-normally distributed and thus inappropriate for Analysis of Covariance (ANCOVA).

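### The covariate rules do not exclude average wound care length, which is known only after dosed sessions, so adjusting for it could bias the ketamine comparison

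*Combined protocol and SAP*

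**What the plan says.** The randomization paragraphs of section 4 (under the heading on tracking consenting and non-consenting patients) list five items on which random assignment should make the arms equivalent. They are the first NAS score, TBSA, "3) the need for surgery; 4) the average length of wound care procedures", and a group of other variables that includes baseline psychological symptoms. A measurement time is given for the first score, which precedes the first session, and for the symptom measures, "which will all be assessed at study enrollment before the first target dressing change". None is given for surgery or procedure length.

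The same paragraph says baseline data will be compared between arms at 25%, at 50% and at completion, and related to the core outcomes. It ends: "If necessary, their effect will be taken into consideration in planned analyses". The next paragraph counts both items among "important but extraneous variables such as procedure duration and other aspects of wound care, rehabilitation and surgery".

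The Data Analysis Plan in section 7 states, for the pain analyses and again for opiate sparing: "If relevant covariates are not balanced by the randomization, or confounds are distributed unevenly across groups, they will be included in the models as covariates". Neither statement requires the variable to have been measured before dosing.

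The second check point is put at "37-47/group) of study completion to assess presence of balancing issues". Section 7 gives "a total sample size of 74-94 participants (n= 37-47 per Condition" as the whole sample.

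**The concern.** Randomization balances what is fixed before treatment. It does not balance what treatment can change. An average over wound care sessions cannot be known until those sessions have been run under ketamine or saline, and section 1 (Dosing) leaves it to the nurse to decide when each session is over. If ketamine alters session length, a difference between arms is a consequence of treatment, and adjusting for it removes or distorts part of the effect that the primary comparison should estimate.

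The documents do not show such an effect, but a route for one exists: the PRN section sets a waiting interval of at least 15 minutes between fentanyl injections, so poorer analgesia could lengthen a session. The adjustment is triggered by imbalance, and a ketamine effect on duration is one way to create imbalance. Chance is another.

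At stake are the size and power of the pain comparison, and in the same way the opiate-sparing comparison.

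**Working it through.** **1. The plan's own sample size.** Inputs from the corrected (5.5-day) sample size section: difference 2.0, SD 4.0, ICC 0.7, 11 sessions, 80% power, alpha 0.05. Sidedness is not stated; two-sided is assumed.

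- Design effect = 1 + (11 − 1) × 0.7 = 8.0, as stated.
- SD of a participant's mean = 4.0 × √(8.0/11) = 3.41 (variance 11.64).
- Required n per arm: 46 by the normal approximation, 47 by the t distribution. The stated 47 per arm (94 in total) reproduces.
- SE of the difference = 3.41 × √(2/47) = 0.704. Power for 2.0 points is 80.3% (noncentral t).

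**2. Adjusting for session length.** The documents give neither the effect of ketamine on session length nor the relation of length to pain, so both are assumed. Let ketamine shorten mean session length by *a* SD, and let pain rise by *b* NAS points per SD of length within arm. The total effect stays at 2.0 and the within-arm SD of participant means at 3.41.

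- Adjusted effect = 2.0 − *a* × *b*
- Residual SD = √(11.64 − *b*²)
- SE = residual SD × √(2/47) × √(1 + *a*²/4), where the last factor reflects the correlation between length and arm

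| *a* | *b* | Adjusted effect | Residual SD | SE | Power |
|---|---|---|---|---|---|
| 0.5 | 1 | 1.5 | 3.26 | 0.693 | 57% |
| 0.5 | 2 | 1.0 | 2.76 | 0.588 | 39% (about 40%) |

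The residual SD has to be recomputed: with *b* = 2, length explains 4/11.64 = 34% of the variance in participant means, and keeping the SE at 0.704 would understate the power.

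A wider range, with *b* from 0.5 to 1.5:

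- *a* = 0.25: adjusted effect 1.63 to 1.88, power 71% to 75%
- *a* = 0.5: 1.25 to 1.75, power 48% to 68%
- *a* = 0.75: 0.88 to 1.63, power 25% to 58%

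Simulation of 4,000 trials with *a* = 0.5 and *b* = 1 gave 1.99 points and 81% power unadjusted, against 1.50 points and 57% adjusted.

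**3. When nothing is lost, and when the sign reverses.** With *a* = 0 the adjusted effect stays at 2.0. If ketamine lengthened sessions by 0.5 SD, the adjusted effect would be 2.0 + 0.5 × 1 = 2.5, or 2.0 + 0.5 × 2 = 3.0, which is too large. An unmeasured cause shared by session length and pain, such as wound severity, could also push the bias either way once ketamine affects length.

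**4. Need for surgery.** The section on requested changes describes some patients going to surgery within the 7 days, as an example of why length of stay is hard to predict at admission. That dates the operation, not the judgement that one is needed.

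**5. Check points.** 25% of 74 and 94 is 18.5 and 23.5; 50% is 37 and 47. So 19-24 and 37-47 are totals. Read as per-group counts, the second check would fall at 2 × 37 = 74 to 2 × 47 = 94 participants, which the same paragraph gives as completion.

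**The case against.** The strongest reply is that the plan means baseline variables only. The sentence on balance checks opens with baseline data, the next sentence refers back to the same data, and the Data Analysis Plan speaks of confounding baseline variables and gives age, gender and TBSA as examples. No sentence says that procedure length or surgery will be a covariate, adjustment in the randomization text is only if necessary, and that text expects random assignment to deal with both. This stands as far as it goes: a reader may not conclude that the plan commits itself to adjusting for session length. It does not close the gap, because procedure length is itself in the list to be balanced, no pre-dose version of it could exist, and the imbalance rule carries no timing limit.

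A reader might also infer that both variables are observed only after dosing. That is supported for average procedure length. For need for surgery it is not: a judgement recorded before randomization would be a legitimate covariate, and the documents do not say when the judgement is made.

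Nor do the documents say that ketamine shortens sessions or that nurses finish sooner when pain is lower. The mechanism and the sizes above are assumptions.

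Finally, a reader might infer from the check-point counts that imbalance could not be detected during enrolment. That goes too far. The per-group label is most likely a slip, and even read literally the first check (38-48 participants) falls at about half of 74-94. Section 7 also raises the target to 100, so 74-94 need not be the end of enrolment.

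**Conclusion.** The concern holds as a gap in the covariate rules. The plan places a post-dose quantity, average procedure length, among the variables to be balanced and possibly taken into account, and nothing bars it from the pain or opiate-sparing models. Bias is possible and not certain: it needs the wider reading of the rule, a decision to adjust, and an effect of ketamine on session length. Under the assumed 0.5 SD shortening and 1 or 2 NAS points per SD, the adjusted effect falls by a quarter or a half and power drops from about 80% to about 57% or 40%. With no effect on length nothing is lost; with lengthening the error runs the other way. For need for surgery the defect is an undefined ascertainment time. The check-point counts are a labelling error that needs correction and do not show that balance monitoring fails.

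**What to change.** 1. In the randomization text and in both covariate statements of the Data Analysis Plan (pain and opiate sparing), state that only variables recorded before the first study dose may be adjustment covariates, for example first pre-session NAS and TBSA.
2. Remove average procedure length from the balance and adjustment list, and report it by arm as a post-randomization result.
3. Keep need for surgery in the list only if it is defined as a judgement recorded before the first dose; otherwise report it by arm as well.
4. Relabel the check points as about 19-24 and 37-47 participants in total.

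The cost is wording, plus one pre-dose data item if need for surgery is kept. The sample size does not change: 47 per arm still gives about 80% power for the 2.0-point total effect under the plan's inputs.

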# 4. Real-Time Data Collection: In-Person And Telephone:

- a) Standard Assessment Approach: There will be an assigned RA for each participant enrolled in this study (primary RA). The primary RA will meet the participant in person, at a minimum, prior to each wound care session to establish comfort and rapport and to address and concerns. Typically, the primary RA will conduct the data collection in person, in the wound care area and in view of the participant to facilitate ongoing rapport, and to clearly demonstrate professional and mutual commitment to patient/participant concerns and contributions.
- b) Problem: There are several circumstances that will routinely arise in the course of this study that make it nearly impossible to arrange for all assessments to be conducted by the primary RA in the room of the participant. Such circumstances include external factors (e.g., inclement weather, illness) and multiple personal obligations (work/school/family/other responsibilities). There are also study-specific logistic (split shift, Day shift: ~9AM-1PM, and, Evening shift: ~9PM-1AM; weekend shifts) and design requirements (repeated measures: 7 days, twice-daily wound care) that obviate expectations for the primary RA to be present in-hospital, in wound care for each participant.
- c) Back-Up Approach and Evidence: Review of the literature indicates that there is substantial consensus for comparable precision, validity and reliability of standardized measures collected via telephone administration, in-person administration and self-completed / mailed-in (Improved Outcome Methods in Longitudinal Studies of Acute Lung Injury; Burn Model Systems; Bellamy, Campbell, Hill, Band, 2002).
- d) Solution: The equivalence of results in studies contrasting in-person versus telephone administration of assessment provides sufficient rationale for the Ketamine RCT's utilization of telephone data collection by trained RAs using structured, psychometrically sound measurement tools.

e) In order to ensure privacy in data collection, and security in data entry, the following specifications are included in the procedure for remote data collection. The RA, when remotely assessing participants via telephone, they will wear headphones, and will call in from a sound-isolated, disruption free, and locked work space, where neither the inquiries made by the RA, nor the responses made by the participants will be audible to anyone else. The data will be directly entered into REDCap using a Hopkins IT-prepared device. This enters data directly into the REDCap server and does not require nor allow for data recording on personal devices according to the senior software engineer at the SOM ICTR at JHB: [name] ([contact], cc'ed).

# **Concomitant and Supportive Therapy:**

The administration of any other therapies intended to treat pain during and between the targeted dressing changes will be permitted, as determined by the provider, and will be reported to and recorded by the study coordinator. Similarly, the use of other concurrent investigational drugs is allowed and is to be reported and recorded by the study coordinator.

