# **Exclusion Criteria:**

- Requiring endotracheal intubation and sedation
- Diminished Level of Consciousness / Cognitive Function:  $MMSE \leq 20$ .
- Diminished Capacity Incapable of providing informed consent (reason(s) to be listed).
- PMH: Insensate to pain in burn wound location (e.g., SCI; peripheral neuropathy)
- Safety: Contra-indication (e.g., potential drug interactions, medical comorbidities)
- 1. Protocol: Study Design, Dosing & Duration:
  - a. Design: Triple blind (nurse, patient, RA) Randomized Controlled, parallel group Trial (RCT):

Group 1: Usual Care plus Saline placebo (IV Fentanyl plus Saline slow infusion administered via programmed pump)

Group 2: Usual Care plus Ketamine augmentation (IV Fentanyl plus low-dose Ketamine slow infusion administered via programmed pump)

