## b. PRN Fentanyl Medications: Pain Assessment Before, During and After Wound Care Session.

Criteria for PRN: The study protocol will use the JHBC standard-of-care method for rating pain and the need for additional analgesic medications before, during and following wound care. That is, as part of standard-of-care, pain is routinely assessed before, during and after wound care by the Registered Nurse/Wound Care Tech (RN / Tech) to determine whether there is a need for additional pain medications. This standard-of-care pain rating process will be applied in this study protocol. The RN / Tech will ask participants to rate their pain before the ketamine / placebo loading dose administration approximately 10 minutes prior to the start of each wound care session, during the wound care session when clinical observations suggest pain assessment is indicated, and, after wound care session ends. At each of these times, when the RN / Tech asks participants to rate their present pain intensity (PPI) on Numeric Analogue Scale (NAS: 0-10), those participants who rate their PPI/NAS as  $\geq$ 7/10, or, whose pain severity has risen  $\geq$ 2/10, will be asked the following:

- i. The RN / Tech asks the participant "Do you need additional pain medication?"
- ii. If the participant says "Yes" then the PRN medication is administered (1 mcg/kg-based fentanyl, injected).
- iii. If participant says "No" then the PRN medication is not administered.
- iv. The RA will record, on a standard form, the PPI/NAS that the RN was given, whether a PRN was offered (Y/N), whether the participant accepted (Y/N), what drug / dose /

delivery method were utilized, and elapsed time since loading dose or, the previous PRN analgesic administration.

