# d. Justification of why participants will not receive routine care or will have current therapy stopped. $N\!/\!A$

**e. Justification for inclusion of a placebo or non-treatment group.** (see above background and design for purpose of saline placebo and blinding, respectively). There is no "non-treatment group" - both groups receive usual care - fentanyl. Blinding by pharmacy preparation of the drug and delivery system in identical, nondescript pump formats for both groups is standard in drug trials in order to prevent bias to confound prescription, observations, data recording, etc. There are actually 3-levels of blind in this project: Nurse at bedside, Patient/participant, and, research assistant.

**f. Definition of treatment failure or participant removal criteria.** Should a patient decide to withdraw, all efforts will be made to complete and report the observations as thoroughly as possible. Reasons for premature withdrawal may include:

- Disease progression
- Unacceptable adverse events.
- Intercurrent illness that prevents further administration of treatment or would affect assessment of clinical status to a significant degree.
- Initiation of non-protocol therapy for the disease under study.
- Non-compliance with protocol or treatment.
- Subject becomes pregnant.
- g. What happens to participants receiving therapy when study ends or if a participant's participation in the study ends prematurely

When the study ends or when a participant's participation ends prematurely, he/she will continue to receive usual care treatment.

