# **Participant Dropout**

Dropouts and participants whose wound care ends or changes substantially prior to the anticipated 7day study period will be handled on an intent-to-treat manner in all key analyses with the last data obtained treated as the endpoint for that participant. Reasons for dropout will be recorded and contrasted across group.

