All patients enrolled in the study will be patients at the Burn Intensive Care Unit (BICU) and will be under the ongoing care of the Burn Surgery and Critical Care Medicine Services. All patients in the BICU are at risk for delirium from multiple sources and are assessed and monitored for this condition as part of regular nursing and physician assessments of the patient's mental status. However, to address the question regarding the possibility that subjects who receive Ketamine will have a higher incidence of hallucinations/delusions, we will keep a daily tally of such experiences in subjects' research charts (i.e., the presence or absence of hallucinations/delirium in addition to the severity of these symptoms, should they exist) using the Side Effect Measure of Opiates and Ketamine (see Measures) as well as a list of other potential causes of the delirium / hallucinations (e.g., benzodiazepines, alcohol withdrawal). We will conduct post hoc analyses to address the relative frequency and severity of these phenomena in the ketamine versus usual care "control" arms of the study.

b. Steps taken to minimize the risks.

Assessments: Twice during each shift, all patients on the BICU are scored using the nurseadministered CAM-ICU and the RASS. These are recorded in EPIC and changes reported to providers and to the following shift. The study team will assess potential side effects using the patented Side Effect Measure for Opiate and Ketamine (SEM-OK; Janssen). The SEM-OK will be administered prior to day 1, session 1, and after session 1 on days 3, 5 and 7. The RA and the Co-Investigator provider present will rate the SEM-OK.

Low-Dose, Slow Infusion Ketamine: In order to minimize the psycho-mimetic risks, the ketamine+UC will be delivered in a sub-anesthetic, low dose, slow infusion preparation (see above). The dose, route, duration time of infusion have been established per study protocol and as prescribed by and monitored by the study Co-PI ([name], CCAM), the JHBMC Pharmacist ([name]), Burn Center anesthesiologist ([name], CCAM), Burn Center attending surgeon ([name], Burns & Plastic Surgery), or, under the direct, supervisory and evaluative authority of these physicians, the Burn Fellows, or the burn center mid-level providers (PA, NP) and as monitored by the professional nursing staff of the Johns Hopkins Burn Center. The psycho-mimetic risks will be monitored as noted above using the Side Effect Measure of Opiates and Ketamine (see Measures).

3.

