# Most licensed staff of the Johns Hopkins Burn Center are trained in Advanced Burn Life Support (ABLS)

Cardiac and pulmonary safety, efficacy and side effects of Ketamine + Usual Care and the Usual Care regimens will be digitally monitored with alarm set, as well as monitored by the Nurse performing the procedure, the Physician Assistant and/or Nurse Practitioner and Burn Fellow assigned to the Burn Intensive Care Unit.

The Confusion Assessment Method for the ICU (CAM – ICU) and the Richmond Agitation and Sedation Scale (RASS) will be used twice during each shift within one hour after dressing change for assessing the arousal, confusion and agitation, which is consistent with current Burn Unit protocol. The Side Effect Measure for Opiates and Ketamine will be scored once per session for each day shift by the RA and provider at hand.

a. Plan for reporting unanticipated problems or study deviations. All unanticipated problems or study deviations will be reported to the IRB. Furthermore, [name] will serve as the Independent Medical Monitor for the Ketamine study. He has agreed to serve in this capacity.

As the independent medical monitor he will have the specific power to do the following:

- Stop this research study in progress
- Remove individual from this study
- Take any steps to protect the safety and well-being of participants until the IRB can assess the problem or event
- a. Legal risks such as the risks that would be associated with breach of confidentiality. Minimal. Subjects will all be patients at the BICU
- b. Financial risks to the participants. None

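### The protocol allows other investigational drugs and any provider-chosen pain therapy, and nothing specifically keeps non-study ketamine out of either arm

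*Combined protocol and SAP*

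**What the plan says.** Two sentences under Concomitant and Supportive Therapy set the rule. The first, on analgesia, reads "The administration of any other therapies intended to treat pain during and between the targeted dressing changes will be permitted"; the provider decides, and the study coordinator is told and makes a record. The second says that "the use of other concurrent investigational drugs is allowed and is to be reported and recorded by the study coordinator". Supportive Care Guidelines adds a general permission for medication needed for care and safety, provided it is documented in the medical record.

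The rescue rules in Section 4, PRN DOSE (Fentanyl), point the same way. After a PRN fentanyl dose that does not help, or after three doses, staff may turn to an alternative medication. The document does not name that medication, and the nurse and provider choose it.

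The design contrast in the Abstract is fentanyl plus saline against fentanyl plus ketamine, and the Abstract names safety among the things to be evaluated.

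**The concern.** Drug trials usually restrict two kinds of co-treatment: another unlicensed or experimental agent, and the test drug given outside the protocol. This plan expressly permits the first, and its general wording does not except the second. Four things are at stake.

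- **Attribution and interactions.** Section 8 asks staff to keep "a list of other potential causes of the delirium / hallucinations (e.g., benzodiazepines, alcohol withdrawal") alongside a daily tally of such events. A second investigational drug adds a candidate cause and a possible interaction. If the other trial is itself blinded, recording participation does not show what the patient received.
- **Pain contrast.** Ketamine given to saline patients would move the difference in pain scores toward zero.
- **Opiate sparing.** The effect here is less direct. Specific Aim #2 counts requests for extra analgesic, and a request answered with ketamine still counts. Only later requests that it prevents, or ketamine given without a request, would alter the count.
- **Dose stacking.** In the ketamine arm, non-study ketamine would add to the study dose. The nursing policy in Section 8 says the prescribing provider does not know the arm, so the extra dose could be ordered without knowledge of the study dose.

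**Working it through.** This is mainly a reading of the text, so the test is whether any other section closes what Concomitant and Supportive Therapy leaves open.

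**1. Candidate restrictions**

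- Exclusion Criteria: "Safety: Contra-indication (e.g., potential drug interactions, medical comorbidities"). This applies at entry. It mentions neither co-enrolment nor ketamine, and the inclusion criteria do not either.
- Section 4.f, removal criteria: "Initiation of non-protocol therapy for the disease under study" is one of several reasons for withdrawal that may apply. It is not a prohibition and names no drug.
- Section 8, independent medical monitor: may "Remove individual from this study". This is a discretionary power, with no rule on either kind of drug.
- PRN Fentanyl Medications: the research assistant logs "whether the participant accepted (Y/N), what drug / dose" and related details. This documents exposure but does not prevent it.
- Section 8, nursing policy: nurses may not adjust the study infusion. A separate ketamine order is not covered.
- Section 8, pharmacy: committee approval covers ketamine in this protocol. It does not say that ketamine is unavailable outside it.

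None is specific to investigational drugs or to non-study ketamine.

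**2. Is non-study ketamine plausible at this site?**

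For: the haemodynamic items in Section 8 rely on the attendings' clinical experience with low-dose ketamine in burn patients, and Section 11 (Costs) contemplates study medications being prescribed in routine pain management, without naming ketamine separately. Against: Section 3 says fentanyl is by far the preferred analgesic in this unit. So it is plausible, at an unknown rate.

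**3. Which pain ratings could it reach?**

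The PRN criteria are first applied before the loading dose, about 10 minutes before wound care. The stated wait after a PRN dose is at least 15 minutes. An alternative drug could therefore follow at about −10 + 15 = +5 minutes, which is 5 minutes into wound care. Ratings are taken at onset and every 10 minutes, so the first 10-minute rating could already be affected. Therapy between sessions is also permitted, so a later session could be affected from its start.

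**4. Does the sample size allow for it?**

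Inputs from the Corrected Sample Size Estimate: difference 2.0, SD 4.0, 80% power, alpha 0.05 (two-sided assumed), 11 observations per patient, within-patient correlation 0.7.

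- Design effect: 1 + (11 − 1) × 0.7 = 8.0.
- Two-sample t-test with independent observations: 64 per arm.
- 64 × 8.0 / 11 = 46.5, so 47 per arm, as the plan states.
- The 7-day version (SD 3.0, 14 observations, design effect 10.1) also reproduces: 37 × 10.1 / 14 = 26.7, so 27 per arm.

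Neither calculation has a term for ketamine in the saline arm. If a share c of saline patients received the full ketamine effect, the expected difference would be 2.0 × (1 − c). The documents give no value for c and no basis for assuming a full effect, so the calculation stops there.

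**The case against.** The strongest reply is that this is a pragmatic comparison of usual care with and without ketamine. Burn patients in severe pain need flexible analgesia, and provider discretion with recording is defensible. The word *other* in the permission can be read as other than the study regimen, which would leave ketamine outside it. Section 8 records approval of ketamine for this protocol and gives no example of non-study ketamine used as wound-care rescue. Coordinator records, the medical chart, the list of alternative causes and the monitor's powers all help attribution.

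Much of this stands. Flexible rescue should remain, and the ketamine part rests on general wording rather than on express permission. But a reading that must be argued for is not a rule a bedside provider can follow, and the investigational-drug sentence is explicit.

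Three stronger readings are tempting and are not supported:

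- **A conflict with the removal criteria.** A reader might infer that a therapy permitted in one place triggers withdrawal under Section 4.f, after which Participant Dropout applies, "with the last data obtained treated as the endpoint for that participant". A therapy that the protocol permits is arguably not non-protocol therapy, the listed reasons only may apply, and Section 4.f asks for observations to be completed as fully as possible after withdrawal.
- **A quantified loss of power.** This would need a contamination rate and a size of effect in contaminated patients. The documents give neither.
- **A dose figure as the size of the problem.** The milligrams per kilogram that can be worked out from the dosing section are the planned study dose. They say nothing about how much non-study ketamine anyone would receive.

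**Conclusion.** The concern holds as a minor point. Other investigational drugs are expressly allowed. Provider-chosen analgesia is allowed in terms that do not except non-study ketamine, and no other section specifically restricts either. The size is unknown.

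Co-enrolment does not bias the randomised comparison in expectation. What it costs is clean attribution of adverse events and freedom from possible interactions. Non-study ketamine could dilute the pain contrast in the same session or a later one, and in the active arm it would add to a blinded dose.

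The conclusion assumes that co-enrolment or non-study ketamine could occur at this site, which the documents make plausible but do not show. The dose-stacking point also assumes that the ordering provider is blinded. The nursing policy in Section 8 says so, but Section 4.c (Blinding) and Section 4.e list only nurse, patient and research assistant.

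**What to change.** 1. Under Concomitant and Supportive Therapy, replace the investigational-drug sentence with: *Participants should not receive another investigational drug from consent through the last study session; any such use is recorded and reported by arm, and the participant stays in follow-up and in the intent-to-treat analysis.*
2. Add to the Exclusion Criteria: *Current treatment in another interventional drug trial.*
3. In PRN DOSE (Fentanyl) and in Concomitant and Supportive Therapy, add: *Non-study ketamine is not to be used for wound-care or between-session analgesia through the last study session unless the provider documents that other rescue options have failed or are contra-indicated. Any use is recorded, reported by arm, and does not end participation or data collection.*

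The cost is one replaced sentence, one exclusion and one short rule in two places. Any co-enrolled patients become ineligible (number unknown), and the provider's choice of rescue is slightly narrowed, though ketamine remains available where other options fail. The restriction ends at the last study session, so it does not cover the period up to the 1-month secondary outcomes.
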